	safety analysis includes calculation of frequencies and rates of complications and serious adverse events together with corresponding 95%-confidence intervals. In addition, tolerability and dosing will be described by numbers of patients in whom treatment was given as planned, delayed or permanently stopped. Detailed procedures of the interim and final analysis will be specified in separate Statistical Analyses Plans (SAP), which will be finalized before interim/final database lock.
Trial duration	Overall duration: 60 months Minimal Follow-up: 24 months FSI (first subject in): 01/2023 50% accrual: 09/2024 LSI (last subject in): 01/2026 LSO (last subject out): 01/2028
Participating sites	University Hospital Heidelberg - HIT University Hospital Dresden - OncoRay

Flowchart

Treatment schedule	baseline visit	weekly during RT	end of RT	FU 1 6 weeks post RT	FU 2 3 months post RT	FU 3 6 months post RT	FU 4 9 months post RT	FU 5 12 months post RT	FU 6 15 months post RT	FU 7 18 months post RT	FU 8 21 months post RT	FU 9 24 months post RT
Informed consent	✓											
Inclusion/exclusion criteria	✓											
Demographic information	✓											
Anamnesis/clinical examination	✓			✓	✓	✓	✓	✓	✓	✓	✓	✓
randomization	✓											
AEs und SAEs	✓	✓	✓	✓	✓	✓	✓	✓	✓	✓	✓	✓
Symptoms/toxicity	✓	✓	✓	✓	✓	✓	✓	✓	✓	✓	✓	✓
MRI	✓			✓	✓	✓	✓	✓	✓	✓	✓	✓
QLQ-C30 & QLQ-BN20	✓		✓			✓		✓				✓
PRO-CTCAE	✓	✓	✓	✓	✓	✓	✓	✓	✓	✓	✓	✓
(Cognitive assessment)	✓		✓			✓		✓				✓

1 Introduction

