6.5 Follow-up

Trial follow-up starts six weeks after completion of radiotherapy. Further follow-up exams are scheduled every three months for a period of two years. The following parameters will be assessed:

- Contrast-enhanced MRI of the brain
- Clinical status
- Toxicity (according to CTCAE 5.0)
- Patient reported outcome of CTCAE (PRO-CTCAE)
- Quality of life (only after 6, 12 and 24 months)

7 Assessment of efficacy parameters

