7.1.2 Progression free survival

Progression-free survival (PFS) is one of the secondary endpoints of the trial. Progression-free survival will be counted from the first day of radiotherapy treatment until the date of the first event of either progression or death due to any cause. Patients alive without progressive disease at the time of data analysis will be censored at the time of the most recent follow-up visit. Radiological responses will be classified as follows:

Complete remission (CR): Remission of all solid tumor lesions on CT or MRI without worsening of neurologic status

Partial remission (PR): at least 50% remission of the solid tumor lesion on CT or MRI without increase in steroid medication and without worsening of the neurologic status

Stable disease (SD): Remission of the solid tumor on CT or MRI of less than 50% or progression of the solid tumor on CT or MRI of less than 25%, without increase in steroid medication or worsening of the neurologic status

Progressive disease (PD): Increase in solid tumor of 25% or more or development of a new lesion

Progression-free survival and its distinction from radiation induced contrast enhancement will be assessed as defined hereunder:

Follow-up assessments (including MRI or CT) will be performed as described until disease progression (even after the end of the study). Special attention should be given so as to avoid tissue reaction to radiation treatment to be classified as tumor or disease progression. Such variations in post-radiotherapy imaging may continue for months, and may be accompanied by clinical signs and symptoms. In addition, surgical procedures may cause increased contrast uptake which should be differentiated from tumor progression. The clinical follow-up must dictate how the initial progression of the lesion should be labeled. If the course of events shows that true progression indeed occurred, the date of the first increased is to be considered as the date of progression. The principal investigator may be contacted for further discussion on a case by case basis.

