7.1.3 Overall survival

Overall survival (OS) is one of the secondary endpoints of the trial. The duration of survival is the time interval between initial diagnosis (date of the neuropathology report) and the date of death due to any cause. Patients not reported dead or lost to follow-up will be censored at the date of the last follow-up examination.

8 Assessment of safety parameters

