12.3.3 Analysis of the secondary endpoints

The secondary endpoints overall survival and progression-free survival will be analyzed using Kaplan-Meier-Curves. The 1-year and 2-year survival rates as well as the median survival rate will be provided alongside two-sided 95%- confidence intervals. A Cox

regression frailty model adjusting for the fixed factors treatment and dose, and the frailty factor center will be conducted to compare the two treatment groups.

Missing values in the items of PRO-CTCAE, QLQ-C30 and QLQ-BN20 will be handled as described in the scoring manuals of the QoL measures. Further missing values will be documented and frequencies will be described with descriptive methods.

The secondary endpoint neurocognition (MoCA) will be analyzed using a non-parametric Van Elteren Test stratified for center.

The other secondary endpoints and the patients` characteristics will be displayed by descriptive measures grouped by treatment group. Continuous variables will be described using number non-missing values, mean, standard deviation, median, Q₁, Q₃, minimum and maximum. In addition, t-test between treatment groups will be performed.

For binary or categorical variables absolute and relative frequencies will be provided. Furthermore, two-sided 95%- confidence intervals will be calculated and chi-square tests between treatment groups.

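### The OS rule sets no cut-off for deaths but censors survivors at their last examination, so the Kaplan-Meier tail and median are biased downward if deaths after that examination are counted

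*Protocol*

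**What the plan says.** Protocol section 7.1.3 defines OS as "the time interval between initial diagnosis (date of the neuropathology report) and the date of death due to any cause". It gives no date after which a death stops counting. For everyone else, "Patients not reported dead or lost to follow-up will be censored at the date of the last follow-up examination". I read this as covering both patients not reported dead and patients lost to follow-up.

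The examinations that set the censoring date come from two places. Section 6.5 says "Further follow-up exams are scheduled every three months for a period of two years", and the visit table ends at FU 9, 24 months after radiotherapy. Section 7.1.2, on PFS, adds: "Follow-up assessments (including MRI or CT) will be performed as described until disease progression (even after the end of the study"; that is, assessments go on for patients without progression. The synopsis gives "Minimal Follow-up: 24 months FSI (first subject in): 01/2023 50% accrual: 09/2024 LSI (last subject in): 01/2026 LSO (last subject out): 01/2028", so 24 months is a minimum and the calendar spans 60 months.

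The planned output is in section 12.3.3: "The 1-year and 2-year survival rates as well as the median survival rate will be provided alongside two-sided 95%- confidence intervals". A Cox frailty model compares the arms. Section 12.4 asks for the same rates and median at the interim analysis.

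**The concern.** Kaplan-Meier estimation needs the people at risk at any time to represent everyone still alive then. Under section 7.1.3 the two outcomes are recorded over different windows. A patient who dies after the last examination stays at risk until death. A patient who is alive, even if known to be alive by telephone or letter, leaves the risk set at the last examination. Beyond that examination the risk set can therefore be selected on the outcome.

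Three groups are exposed: patients past FU 9 if their examinations end there, patients who have progressed (section 7.1.2 continues assessments only until then), and patients lost to follow-up.

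What is at stake is the median OS with its confidence interval, in a population that section 1.2 expects to become long-term survivors. The likely correct report is that the median was not reached. The rule could instead produce a number.

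**Working it through.** The protocol states no OS figure (no median, event count or power), so there is none to reproduce. The only stated figure that uses the death assumption is the sample size: 98 / (1 - 0.18) = 119.5, rounded up to 120, as stated.

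**Inputs from the protocol.** Entry from 01/2023 to 01/2026 (36 months) and last subject out 01/2028 (month 60), from the synopsis. Visits to 24 months after radiotherapy (6.5). 8% deaths and 10% drop-out after 12 months, and 120 patients (section 11).

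**Assumptions not in the protocol.** Uniform entry, constant death hazard, 1.5 months from entry to end of radiotherapy, the share of late deaths that is reported (25-100%), the lag from diagnosis to entry, and the progression rates.

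**Truth under 8% dead by 12 months.** Hazard h = -ln(0.92)/12 = 0.00695 per month. S(24) = 0.92² = 0.846. S(36) = 0.92³ = 0.779. Median = ln 2 / h = 99.8 months.

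**Hand check of the worst case.** Take the clock at entry, no drop-out, FU 9 at 1.5 + 24 = 25.5 months, no later examinations, and later deaths counted.
- S(25.5) = exp(-0.00695 × 25.5) = 0.838.
- After 25.5 months only patients whose later death is reported remain at risk. The chance that a death at time t falls before month 60 of the trial is proportional to (60 - t). Treating the hazard as flat over this stretch, the curve is about 0.838 × ((60 - t)/34.5)², where 34.5 = 60 - 25.5.
- At 36 months: 0.838 × (24/34.5)² = 0.41, against a true 0.779.
- It crosses 0.5 at t = 60 - 34.5 × √(0.5/0.838) = 33.3 months.
- The share of late deaths reported cancels out of this expression. That is why 25% reporting does nearly the same damage as 100%.

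**Simulation** (one large sample per case for S and the median; 200 trials of 120 patients for how often a median is reached; 8% dead by 12 months, 10% drop-out, clock at entry):

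| How deaths and visits are handled | S(24) | S(36) | Median (months) | Median reached, n = 120 |
|---|---|---|---|---|
| Full ascertainment to month 60 | 0.847 | 0.779 | not reached | 6% |
| Visits stop at 24 months, 25-100% of later deaths counted | 0.838-0.843 | 0.38 | 32-33 | 92-100% |
| 3-monthly visits continue for all | 0.840 | 0.760 | 58.6 | 16% |
| Deaths counted only within the visit window | 0.847 | no follow-up | not reached | 0% |

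With 8% dead by 24 months instead, the second row gives a false median of about 34 months against a true 199.5.

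**Examinations stop at progression.** With an assumed median of 36 months to progression and 18 months from progression to death, and all deaths reported, S(24) is 0.843 against 0.864 under full ascertainment. S(36) is 0.691 against 0.750. A median of 49 months appears where full ascertainment reaches none. With slower rates (60 and 24 months), S(24) is 0.920 against 0.930 and S(36) is 0.832 against about 0.863; a median of 58.8 months appears where none is reached.

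**Clock at diagnosis, as section 7.1.3 has it.** With an assumed mean lag of 24 months to entry and visits stopping at 24 months, the median is 92, 114 or 137 months when 100%, 50% or 25% of late deaths are reported. Full ascertainment gives 136.

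**The case against.** A reader might infer that after month 24 the trial ascertains deaths only, so that the reported median is bound to be spuriously short. The protocol does not support that. Section 7.1.2 continues assessments until progression, and 24 months is the minimal follow-up, so progression-free survivors can keep gaining later censoring dates. Nor does any section set up general collection of deaths after the last visit. Section 8.1 documents AEs up to 6 months after treatment, and section 8.2 asks for later SAEs only if reasonably related to treatment or study participation. If late deaths do not reach the database, the downward bias goes. The clock from diagnosis also guarantees survival up to enrolment, which lengthens OS. With a 24-month mean lag and 25% reporting the shortening vanishes, so the net direction of the reported median is not settled by the censoring rule alone.

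A reader might also infer a biased Cox comparison. The same rule applies in both arms, and no between-arm bias has been shown.

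Finally, cut-off and last-known-alive conventions often sit in the SAP, which is not at hand and to which section 12.3.4 defers further details.

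These points make the bias conditional and limit its weight; they do not make the rule sound. Section 7.1.3 does state a censoring rule, and that rule is asymmetric. Section 7.1.2 gives no continuing examinations to patients who have progressed, and patients lost to follow-up have none by definition. A late death that becomes known in either group counts as an event, whereas evidence that such a patient is alive adds no time.

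**Conclusion.** The point holds conditionally. If deaths after a patient's last examination are counted, the Kaplan-Meier tail and the median OS are biased downward. The protocol fixes neither whether those deaths will be collected nor how many will be, so the size cannot be read from it. Measured from entry, it ranges from no bias (deaths counted only within the visit window), through a small one (3-monthly examinations continue for all), to a false median of 49 months (examinations stop at progression, all deaths reported) or 32-33 months against a true value of about 100 (visits stop at 24 months, at least 25% of later deaths reported).

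The planned 1-year and 2-year rates are fairly safe: the largest shift above is 0.864 - 0.843, about 2 points. OS is a secondary endpoint. The primary endpoint and the sample size are untouched. It is a modest point, but cheap to close before the interim database lock.

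**What to change.** In section 7.1.3, define one common data cut-off date for the interim analysis and one for the final analysis. Count deaths only up to that date. Censor every other patient at the date last known alive, from any contact, up to the same date. Update vital status for all patients at the cut-off, including those who have progressed or stopped attending, so that survival is sought as actively as death. If vital status is not ascertained for all patients beyond FU 9, neither deaths nor survival time after FU 9 should enter the OS analysis. Report the median as not reached where that is the case.

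Truncating every patient at 24 months after radiotherapy regardless would be a poorer choice. It discards valid follow-up obtained under section 7.1.2, and it is not a common limit on a clock that starts at diagnosis.

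The cost is a few sentences in the protocol and in the SAP, a last-known-alive date in the eCRF, and a vital-status check at each cut-off. Deaths outside the window are listed but not analysed.

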8.1 Adverse events

According to GCP, an adverse event (AE) is defined as follows: Any untoward medical occurrence in a subject administered a pharmaceutical product or treatment and which does not necessarily have a causal relationship with this treatment. An AE can therefore be any unfavorable and unintended sign (including an abnormal laboratory finding), symptom, or disease temporally associated with the use of a medicinal (investigational) product or treatment, whether or not related to the medicinal (investigational) product.

An AE may be:

- New symptoms/ medical conditions
- New diagnosis
- Changes of laboratory parameters
- Intercurrent diseases and accidents
- Worsening of medical conditions/ diseases existing before clinical trial start

- Recurrence of disease
- Increase of frequency or intensity of episodical diseases.

A pre-existing disease or symptom will not be considered an adverse event unless there will be an untoward change in its intensity, frequency or quality. This change will be documented by an investigator. Each AE developing during study treatment or within 30 days after completion of study treatment should be documented up to 6 months after completion of study treatment. The investigator is responsible to perform and consider all required therapeutic measures and methods to follow-up this condition. An event, which occurs in conjunction or association with tumor progression will not be considered an AE or subsequently as an SAE unless more severe than expected.

Following examples will also not be considered as an AE:

- A medical or surgical procedure (the condition that led to the procedures is an AE)
- Situations in which an untoward medical occurrence did not occur (e.g. social and/or convenience admission to a hospital)
- Anticipated day-to-day fluctuations of pre-existing disease(s) or conditions(s) present or detected at the start of the study that do not worsen
- The disease/disorder being studied or expected progression, signs or symptoms of the disease/disorder being studied, unless they are more severe than expected for the subject's condition

The grading of AEs in this trial will be carried out on the basis of the 5-grade scale as defined in CTCAE v5.0:

Grade 1	mild AE
Grade 2	moderate AE
Grade 3	severe AE
Grade 4	life-threatening AE or AE causing disablement
Grade 5	death related to AE

The grading of all AEs listed in the CTCAE v5.0 will be based on the information therein. The grading of all other AEs, i.e. those who are not listed will be performed by a responsible investigator, based on the definition given above.

Surgical procedures themselves are not AEs; they are therapeutic measures for conditions that require surgery. The condition for which the surgery is required may be an AE. Planned surgical measures permitted by the clinical trial protocol and the condition(s) leading to these measures are not AEs, if the condition leading to the measure was present prior to inclusion into the trial.

- AEs are classified as "non-serious" or "serious".

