1.2 Trial rationale

Since patients with low grade glioma are expected to become long-term survivors, the prevention of long-term sequelae is particularly important. In addition to disease progression, also treatment related side effects such as decline of neurocognitive function, endocrine impairment or sensorineural deficits can have a negative impact on patient's quality of life.

Owing to the biophysical properties of protons with an inverse depth dose profile compared to photons and a steep dose fall off to the normal tissue, there is a strong rationale for the use of PRT in the treatment of patients with low-grade glioma. Although data from large randomized trials are still missing there is increasing evidence from smaller prospective trials and retrospective analyses that the expected advantages indeed transform into clinical advantages [5,6].

However, in about 20 % of all patients, late contrast-enhancing brain lesions (CEBL) appear on follow-up MR images 6 – 24 months after treatment [7]. At HIT in Heidelberg and at OncoRay in Dresden, CEBLs have been observed to occur at very distinct locations in the brain and relative to the treatment field. Retrospective analysis has elucidated potential key factors that lead to CEBL occurrence. However, avoidance of CEBLs is hardly feasible using conventional treatment planning strategies. Model-aided risk avoidance denotes the use of model-based CEBL risk calculations as an auxiliary tool for clinical treatment planning: Model-based risk calculations and risk reduction via software-based optimization help the clinician to minimize risk of CEBL occurrence during treatment planning.

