2.2 Secondary objectives

- incidence of radiation-induced brain injuries > CTC^oII
- progression-free survival
- overall survival
- safety
- patient reported outcome (PRO-CTCAE)
- quality of life (QLQ-C30 and QLQ-BN20)

3 Trial design and schedule

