8.2 Serious adverse events

A serious adverse event (SAE) is one that at any dose:

- Results in death
- Is life-threatening (the term life-threatening refers to an event in which the subject was at risk of death at the time of event and not to an event which hypothetically might have caused death if it was more severe)
- Requires subject hospitalization or prolongation of existing hospitalization
- Results in persistent or significant disability/ incapacity

Examples of SAEs that do not need to be reported:

- Medical or surgical procedures (i.e. endoscopy, appendectomy); the condition that leads to the procedure may be an AE
- Situations where an untoward medical occurrence did not occur (social and/or convenience admission to the hospital)
- Anticipated day-to-day fluctuations of pre-existing disease(s) or condition(s) present or detected at the start of the study that do not worsen
- The disease/disorder being studied, or expected progression, signs, or symptoms of the disease/disorder being studied, unless more severe than expected for the subject's condition
- A hospitalization which was planned before the patient consented for study participation and where admission did not take longer than anticipated

Any SAE that occurs outside the SAE detection period (after the 30-day period) considered to be reasonably related to the investigational treatment or study participation have to be documented and reported.

This must be done within 24 hours of the initial observation of the event. The principal investigator will decide if these events are related to the protocol treatment (i.e. unrelated, likely related, and not assessable) and the decision will be recorded on the Serious Adverse Event form, if necessary with the reasoning of the principal investigator. The investigator is obligated to assess the relationship between investigational product and the occurrence of each AE/SAE. A “reasonable possibility” is meant to convey that there are facts/evidence or arguments to suggest a causal relationship, rather than a relationship cannot be ruled out. The investigator will use clinical judgement to determine the relationships. Alternative causes, such as natural history of the underlying diseases, concomitant therapy, other risk factors, and the temporal relationship of the event to the investigational treatment will be considered and investigated.

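### Sections 8.1 and 8.2 and the visit tables set incompatible AE/SAE collection periods, so late non-serious AEs and late SAEs judged unrelated may go unrecorded

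*Protocol*

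**What the plan says.** Four parts of the protocol bear on which adverse events are recorded, and for how long.

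- **Section 8.1 (AEs):** "Each AE developing during study treatment or within 30 days after completion of study treatment should be documented up to 6 months" after completion of treatment. Onset is bounded at 30 days and documentation at 6 months.
- **Section 8.2 (SAEs):** "Any SAE that occurs outside the SAE detection period (after the 30-day period) considered to be reasonably related" to treatment or study participation must still be documented and reported. After day 30 the SAE duty therefore depends on relatedness.
- **Visit tables (synopsis flowchart and Section 6.1):** the AE/SAE row is ticked at baseline, weekly during radiotherapy, at its end, and at every follow-up visit from FU 1 (6 weeks) to FU 9 (24 months). Separate rows for symptoms/toxicity and for PRO-CTCAE carry the same ticks.
- **Section 6.5 (follow-up):** "Trial follow-up starts six weeks after completion of radiotherapy", and "Further follow-up exams are scheduled every three months for a period of two years". CTCAE 5.0 toxicity and PRO-CTCAE are listed among the assessments at these visits.

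The synopsis defines the safety assessment through the type, incidence, severity and relatedness of AEs. Section 12.3.4 analyses laboratory parameters, AEs and SAEs descriptively in the safety set, with rates of complications and SAEs. Section 1.2 places the harm under study late: in about 20% of patients "late contrast-enhancing brain lesions (CEBL) appear on follow-up MR images 6 – 24 months after treatment".

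**The concern.** A site cannot apply both texts as written. One closes AE onset at 30 days after radiotherapy; the other asks for AEs for two years. The protocol does not say which prevails.

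The stated period for the lesions of interest, 6 to 24 months, lies wholly outside the onset window of Section 8.1. The experimental arm receives re-optimised plans, so a late effect other than the anticipated brain lesions is what AE recording should be able to show. If the narrower text is followed, such events reach the AE and SAE tables only when they are both serious and judged related. An analysis plan cannot restore events that were never entered, so this cannot be left to the SAP. If one centre follows Section 8.1 and the other the visit table, AE counts would also differ between centres for reasons unrelated to treatment.

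**Working it through.** No sample size, power or alpha figure is involved. The check sets the visit times against the two limits, and then follows each type of late event through the texts.

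**Step 1: visits against the limits.** Inputs: visit times from the table in Section 6.1; limits of 30 days (onset) and 6 months (documentation) from Section 8.1.

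| Visit | Time after RT | AE/SAE tick | After 30 days | After 6 months |
|---|---|---|---|---|
| FU 1 | 6 weeks = 6 × 7 = 42 days | yes | yes | no |
| FU 2 | 3 months | yes | yes | no |
| FU 3 | 6 months | yes | yes | at the limit |
| FU 4 to FU 9 | 9, 12, 15, 18, 21, 24 months | yes | yes | yes |

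All 9 follow-up visits lie after the onset window, and 6 of 9 lie after the documentation limit.

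**Step 2: can the two texts be read together?** Partly, for the first three visits. FU 1 can pick up an event that began before day 30, and FU 2 and FU 3 can continue its documentation. From FU 4 on this fails: under Section 8.1 no non-serious event is left to record, yet the row asks for AEs as well as SAEs. Section 8.2 makes it hard to treat the 30 days as a loose phrase, because it names a detection period and adds a special rule for what comes after it.

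**Step 3: events starting after day 30.**

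| Event | Under 8.1/8.2 | Under the visit tables |
|---|---|---|
| SAE judged related | recorded | recorded |
| SAE judged unrelated | not required | recorded |
| Non-serious AE, related or not | not required | recorded |

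The last row includes some grade 3 events. Section 8.2 defines seriousness by death, threat to life, hospitalisation or lasting disability, and a severe event need meet none of these.

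**Step 4: the filter on late SAEs.** Under Section 8.2 a reasonable possibility needs facts or arguments pointing to a causal link; failure to exclude one is not enough. Section 1.3 says the lesions often cannot be told apart from tumour progression, and Section 8.1 excludes events tied to progression unless they are worse than expected. Relatedness is thus hardest to judge where inclusion depends on it. The design is described only as observer blind, and Section 8.2 does not say that whoever judges relatedness is blinded.

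**Step 5: other routes to 24 months.** CTCAE toxicity and PRO-CTCAE are scored at each follow-up visit. The lesions are the primary endpoint on quarterly MRI. The "incidence of radiation-induced brain injuries" above grade II is its own secondary endpoint (Section 2.2). None of these depends on the window in Section 8.1. Toxicity is, however, a separate row from AEs and SAEs, and Section 12.3.4 does not name it as a source.

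**The case against.** The best defence is that Section 8.1 does not forbid recording later events. It says how long early ones are documented, and a site that also follows the visit table would collect the rest. Late harm has its own routes as well: related late SAEs, toxicity scores to 24 months, MRI, and the brain-injury endpoint, which as a binary outcome falls under the frequencies, confidence intervals and chi-square tests of Section 12.3.3. Section 12.3.4 also mentions complications, a term not tied to the 30 days, and leaves detail to the SAP.

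Much of this stands, and it rules out several stronger readings that a reader might infer:

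- *The safety tables will omit late toxicity.* This follows only if Section 8.1 overrides the visit tables, which the protocol does not say. Even then related late SAEs remain.
- *A necrosis starting at month 9 is not an AE.* The AE definition in Section 8.1 has no time limit. The 30 days belong to the documentation rule.
- *The triggers in Section 4.5 for considering a stop would miss late events.* They refer to toxicity by grade, and toxicity is scored to FU 9. Nothing links them to the 30-day window.
- *The trial could not show a difference in late brain injury.* That comparison rests on the primary and brain-injury endpoints, not on AE tables.
- *The window covers 30/730 days, about 4% of follow-up, so most late events are lost.* That is a share of time, not of events, and it ignores the other routes.

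The defence does not remove the conflict itself. Section 8.2 supports the restrictive reading, and the other routes would not reliably bring late non-serious AEs or unrelated late SAEs into the AE and SAE tables.

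**Conclusion.** The point holds as an internal contradiction in operative text with a possible, bounded loss of safety data. Sections 8.1 and 8.2 and the visit tables cannot all be followed from FU 4 to FU 9, that is at six of nine follow-up visits.

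On the assumption that Section 8.1 governs, the AE and SAE tables would lack two groups of events starting after day 30: non-serious AEs, including non-serious grade 3 events, and SAEs judged unrelated. The late SAEs that do enter would be selected by a relatedness judgement. If the visit tables govern, nothing is lost.

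The number of events affected cannot be determined. The protocol gives no late AE rates and does not say whether the follow-up toxicity scores feed the safety analysis. The primary endpoint and the brain-injury endpoint are not affected. The matter deserves correction because the affected data are lost at the visit and the remedy is cheap.

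**What to change.** Reconcile Sections 8.1 and 8.2 with the synopsis flowchart and the table in Section 6.1, so that one AE/SAE collection period applies at both centres. The period already in the tables, to FU 9 at 24 months, is the natural choice. Both sections should then state that AEs and SAEs starting after day 30 are recorded whatever their seriousness or judged relatedness.

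In Section 12.3.4, add that events starting after 30 days and the follow-up CTCAE toxicity data enter the safety analysis. Whether acute and late events are tabulated separately can be left to the SAP.

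The cost is a wording amendment and some extra data entry at visits already scheduled, where toxicity is already assessed. Sample size, visit schedule and the confirmatory analysis do not change.
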